Berger et al. 2006 (34)	Combination of 2 randomised, double-blind trial	41 burn patients with mean TBSA of 46%	IV trace element cocktail vs Placebo. Cu: 2.5-3.1 mg/d Se: 315-380 ug/d Zn: 26.2-31.4 mg/d	8-21 days	Plasma Se levels increased with supplementation; Reduced number of infections in supplemented pts (3.5 vs 2 episodes per pt)
Berger et al. 2007 (53)	Prospective, randomized, placebo-controlled trial	21 burn patients with mean TBSA of 45%	IV trace element cocktail vs Placebo. Cu: 3.75 mg/d Se: 375 ug/d Zn: 37.5 mg/d	14-21 days	Plasma Se sig higher in supplement group; Number of infect in first 30 days was sig lower in supplement group (2 vs 4 infections per

					pt); Supplement group had fewer regrafting episodes.
Berger et al. 1998 (36)	Prospective, randomized, placebo-controlled trial	20 burn patients with mean TBSA of 48%	IV trace element cocktail vs Placebo. Cu: 3.75 mg/d Se: 375 ug/d Zn: 37.5 mg/d	8 days	The number of infections were lower in supplement group

Overall the data among adults is promising, but does not identify a specific guideline for selenium supplementation during critical illness. The data among children is scarce and less impressive.

C. Rationale behind proposed research/ benefits to society

The Se status of children with major burns is suboptimal which may increase the incidence of infection. Se requirements during critical illness are not known. Results from this investigation may provide a tool for recommending Se supplements during burn injury.

II. Specific Aims

The hypothesis of this research is that Se supplementation will restore the depressed Se status among children with burn injuries. The secondary hypothesis is that Se status is related to the incidence of infection among pediatric patients with burns.

The specific aims of this research are

1. to determine the impact of supplemental Se needed on plasma Se, Gpx activity, and urine selenium among pediatric patients with burns $\geq 20\%$ TBSA.
2. to determine the association between Se supplementation, biomarkers of Se status and indicators of stress and infection.

III. Subject Selection

All subjects (n = 75) will be recruited from the Shriners Hospital for Children in Boston.

Inclusion Criteria:

- Between 1 and 18 years of age admitted to Shriners Burns Hospital
- TBSA burn of $\geq 20\%$
- Existing catheter
- Enrolled into study within 3 weeks of burn injury

Exclusion Criteria:

- < 1 year or > 18 years of age
- $< 20\%$ TBSA burn

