Prior to initiation of the study, the research nurse will hold an in-service for clinical staff to alert them of the study. A specific research sticker will be placed in the chart to alert clinical staff that the patient is enrolled in this research study. The MD responsible for the care of the patient will write the orders for the supplements. The Pharmacy will prepare all supplements and the nurses will administer them.

C. Data Collection

Plasma and urine Se and plasma Gpx will be measured weekly from the time of admission for a maximum of 8 weeks or until the patient achieves 95% definitive wound closure.

The research nurse will obtain 4 ml or 8ml (8 ml will be drawn instead of 4 ml every other week starting with week 1 for real time analysis) of whole blood off an existing catheter and place it into a trace-element free blood collection tube.

Every other week, when 8 ml of blood is needed, 4 ml will be transferred by the unit assistant to the MGH laboratory for immediate analyses (the MGH lab uses Quest Labs for analysis of selenium). If in the unlikely event that the MGH lab rejects the sample for any reason, another 4 mL blood draw will be collected and sent to the MGH lab for real-time analyses.

Weekly, the 4 ml sample will be transported by the nurse to the clinical research lab (in the same building). In the lab the nurse will use a centrifuge to separate the blood and then pipette the plasma and whole blood into collection vials to be frozen prior to analyses. A 24 hour urine will be initiated the day prior to blood sampling for analysis of urinary Se. Urine will be collected via an existing catheter. If no catheter exists patient will be asked to urinate into a container. If the patient is unable to urinate into a container, the urine sample will not be collected. Infant urine will be collected via diapers. The research nurse will then bring the urine container down to the clinical research lab and aliquot it into 50 ml vials prior to being frozen. Frozen samples are eventually mailed to a commercial laboratory for lab analyses. The PI is certified to ship biological products and all appropriate regulations will be followed.

Culture Data

Wound cultures will be obtained for all patients admitted to the acute care unit at Shriners Burns Hospital, per routine care, on admission. Urine cultures will also be obtained upon admission if one or more of the following criteria are met:

- Symptoms of urinary tract infection (UTI)

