where $Z_{(1-\alpha/2)}$ and $Z_{(1-\beta)}$ represent percentage points of the normal distribution for statistical significance level and power, respectively. The values used were 1.96 for a significance level of 5% and 0.8416 for a power of 80%. The Δ represents the standardized difference (the treatment difference divided by its standard deviation). This was calculated by subtracting the mean plasma Se determined in our pilot study (1.08 $\mu\text{mol/L}$) from the average plasma Se of healthy American children 1.35 ($\mu\text{mol/L}$) and dividing by the standard deviation (0.34). This calculation revealed that 25 subjects are needed per group to obtain 80% power and a significance level of 5%.

All subjects enrolled will be included in the statistical analyses (intent-to treat). A 2-sided statistical test will be used for all analyses and the overall type-I error rate will be controlled at the 5% level. For each dependent variable (plasma selenium, urinary selenium, plasma GPx activity) a 2-way repeated measures ANOVA will be used to examine the difference among groups and over time (primary hypothesis). Tukey's will be utilized as the post-hoc test.

An ordinal logistic regression will be performed to determine the relationship between the incidence of infection (categorized by burn, bloodstream, urinary tract infection, and PNA) and plasma selenium, urinary selenium, plasma GPX, age, initial percent TBSA burned, and treatment group (secondary hypothesis).

Appropriate confounding factors (including but not limited to dietary Se intake, age, sex, race, initial %TBSA, and length of time from burn injury to study enrollment) will be included in the statistical models. All statistics will be completed using SAS software.

VI. Risks and Discomforts

Phlebotomy will be minimal (4 or 8 ml/wk) and will be obtained painlessly through existing catheters or during operative procedures.

Se toxicity is rare. Symptoms include:

- memory loss
- gastrointestinal upset,
- hair loss,
- weakened nails,
- white blotchy nails,
- garlic breath odor,
- metallic taste,
- vomiting,

- sweat
- dermatitis,
- dental defects,
- nervousness,
- mental depression,
- fatigue,
- irritability,
- mild nerve damage,
- Peripheral vascular collapse,
- Internal vascular congestion,
- Hemorrhage,
- Congested and edematus lungs,
- Brick-red color gastric mucosa
- Coma
- Death

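### The infection model treats four unranked infection sites as an ordinal outcome, does not fix time on study, and gives no randomised comparison of infection

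*Combined protocol and SAP*

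**What the plan says.** Section V.D (Selenium Analysis), which also holds the statistical methods, plans one analysis of infection: an "ordinal logistic regression will be performed to determine the relationship between the incidence of infection (categorized by burn, bloodstream, urinary tract infection, and PNA". The named predictors are "plasma selenium, urinary selenium, plasma GPX, age, initial percent TBSA burned, and treatment group (secondary hypothesis". The next paragraph adds covariates through an open list: "Appropriate confounding factors (including but not limited to dietary Se intake, age, sex, race, initial %TBSA" and time from burn to enrolment. The same section says "All subjects enrolled will be included in the statistical analyses", and ends observation at the first of four events: 8 weeks, catheter removal, a long infusion stop, or 95% wound closure.

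On the biomarkers, section V.C says "Plasma and urine Se and plasma Gpx will be measured weekly from the time of admission for a maximum of 8 weeks". Section II expects that "Se supplementation will restore the depressed Se status among children with burn injuries".

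The model has two jobs. Section II states "The secondary hypothesis is that Se status is related to the incidence of infection among pediatric patients with burns", and aim 2 is "to determine the association between Se supplementation, biomarkers of Se status and indicators of stress and infection". So both biomarkers and supplementation are to be related to infection.

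**The concern.** There are three separate problems.

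1. **Outcome.** A proportional-odds model needs ranked levels. The only levels named are four anatomical sites. The infection definitions in V.A, item C, do not rank them, and no level is given for a child with no infection. One category per child also cannot hold two sites or repeat episodes.
2. **Time on study.** A child observed for 8 weeks has more chance of infection than one observed for 2. Days on study are not named in the model. Time from burn to enrolment is a different quantity.
3. **Treatment beside its own intermediate.** If treatment raises selenium and selenium is in the model, the treatment coefficient is an effect at fixed selenium. The plan also does not say which weekly value is used.

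This is the only planned analysis of the secondary hypothesis and of the infection part of aim 2. A real benefit could be reported as no treatment effect, and a selenium–infection association could reflect length of stay.

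**Working it through.** **Inputs from the documents.** 75 children, 25 per arm (IV.B). Plasma selenium difference 1.35 − 1.08 = 0.27 µmol/L, SD 0.34 (V.D). Pilot length of stay 50 ± 40 days (I.B, Table 4). Adult burn trials with 2 to 4 infections per patient (I.B, Table 7). The documents give no infection rate by arm, site mix or selenium–days correlation for these children, so those are assumed below.

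**The plan's own figure.** n = 2(1.96 + 0.8416)² / (0.27/0.34)² = 15.70 / 0.6306 = 24.89, so 25 per group. It reproduces. No power is stated for infection.

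**Step 1: coding order.** Four sites allow 4! = 24 orders. A proportional-odds model, logit P(Y ≤ k) = α_k − β × treatment, was fitted to expected proportions under every order. The odds ratio is exp(β).

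| Assumed case | Placebo | Selenium | Odds ratio over 24 orders |
|---|---|---|---|
| Sites only | 0.25 each | 0.2857, 0.2857, 0.2857, 0.1429 | 0.71, 0.89, 1.12 or 1.41 |
| None lowest, fewer infected on selenium | none 0.40; sites 0.15 each | none 0.475; sites 0.15, 0.15, 0.15, 0.075 | 0.70–0.87 |
| None lowest, same share infected | none 0.40; sites 0.15 each | none 0.40; sites 0.225, 0.15, 0.15, 0.075 | 0.80–1.25 |

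The first row is the second row restricted to infected children (0.15/0.525 = 0.2857; 0.075/0.525 = 0.1429). Dropping the uninfected discards the overall reduction.

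**Step 2: more than one episode.** With mean m, P(≥2) is 1 − e^(−m)(1 + m) under Poisson and (m/(1 + m))² under a negative binomial with dispersion 1. At m = 1 this gives 26% and 25%; at m = 2, 59% and 44%; at m = 4, 91% and 64%.

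**Step 3: days left out.** Simulation, 6,000 trials per cell, 25 placebo and 50 treated (doses pooled). Neither treatment nor selenium affects infection. Treatment raises selenium by 0.27/0.34 = 0.79 SD. Assumed: correlation of days with %TBSA 0.5; infection rate 0.02 or 0.05 per day; days uniform on 7–56, or lognormal with the pilot mean and SD clipped to 11–56. Logistic model of any infection on selenium, treatment and %TBSA, without days:

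| Correlation of selenium with days | Selenium false-positive rate | Median treatment odds ratio |
|---|---|---|
| −0.2 | 6.5–7.3% | 1.08–1.11 |
| −0.3 | 8.2–11.0% | 1.11–1.17 |
| −0.5 (worst-case illustration) | 16.2–23.8% | 1.22–1.35 |

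The treatment odds ratio moves because, at equal selenium, a treated child would have had lower selenium untreated and so tends to stay longer. The treatment test itself rejects in only 4.7–7.2%. With log(days) added, selenium rejection is 4.5–5.5% and the treatment odds ratio 0.98–1.02.

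An ordinal model of counts 0/1/2/3+ (700 runs per cell, uniform days) is more sensitive. At correlations −0.3 and −0.5, selenium rejection without days is 9.7% and 24.1% at 0.02 per day, and 18.9% and 40.7% at 0.05 per day. With log(days) it is 5.3–6.7%.

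**Step 4: treatment and selenium together.** Take log E(episodes) = α + τ × treatment + γ × selenium + δ × %TBSA + log(days). If the benefit runs wholly through selenium, the true τ is 0 while the total rate ratio is exp(0.79γ), with γ per SD. Simulated at correlation −0.3:

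| True total rate ratio | Joint model: treatment rate ratio (rejection) | Treatment and %TBSA only: rejection |
|---|---|---|
| 0.70 | 0.99–1.01 (3.9–4.9%) | 18.8–32.3% |
| 0.60 | same range | 28.3–46.2% |
| 0.50 | same range | 41.4–54.8% |

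The model without selenium recovers the true ratio: 0.70 at one end and 0.50 at the other.

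**Step 5: the replacement under no effect.** Poisson with offset and robust variance rejects for selenium in 4.9–5.9%. For treatment without selenium it gives a rate ratio of 1.00–1.01 and rejects in 4.1–4.9%. With overdispersion 0.5, robust variance holds 5.6–5.9% for selenium, but model-based variance gives 9.2–16.5%.

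**The case against.** The text may mean incidence within each site, for example ordered counts per site. That would make an ordinal model sensible and give zero a place, and the coding-order figures would not apply. This is a fair reading, but no such levels are stated, so the outcome is undefined either way.

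Reversing an order inverts the odds ratio by construction, so part of the 0.71–1.41 spread is relabelling. Once an uninfected level is lowest and infection differs between arms, every order points the same way (0.70–0.87). This stands. Without such a level, though, the plan does not say which end is worse, and the size of the effect still varies with the order.

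The open covariate list permits adding days without contradicting the plan. That is true, but it is not pre-specification. The harm depends on a correlation the documents do not report, and at −0.2 it is small in the logistic illustration.

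Biomarkers belong in a model of selenium status and infection, and nothing says the treatment coefficient will be reported as the randomised effect. This also stands. What remains is that no planned model compares infection between the randomised groups, although aim 2 names supplementation.

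Finally, the simulations pool the doses and mostly use logistic or Poisson models instead of the planned one, and a ratio near 1.0 follows almost directly from assuming full mediation. The figures show mechanism and order of size. They do not forecast this trial's bias.

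**Conclusion.** The concern holds and should be fixed. The specification faults can be read from the text with high confidence: unranked categories, no uninfected level, days on study not pre-specified, and treatment fitted only alongside on-study biomarkers. Their numerical size is much less certain. The false-positive inflation for selenium depends on an unknown selenium–days correlation, and the lost treatment effect is complete only if the benefit acts entirely through selenium. The fault is confined to the secondary hypothesis and the infection part of aim 2.

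**What to change.** **Outcome.** Define it as the number of infection episodes per child after randomisation, with zero as a value. Analyse it by Poisson regression with robust variance, or negative binomial, with log(days observed) as offset. An ordinal model of 0, 1, 2, 3+ with days as covariate is an acceptable alternative. Report site-specific rates descriptively.

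**Two models.** (A) Treatment group with age, initial %TBSA and time from burn to enrolment, reported as the randomised comparison. (B) Selenium biomarkers with the confounders listed in V.D, labelled as an association. If treatment stays in (B), do not report its coefficient as a treatment effect.

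**Definitions to add.** How a new episode is told from a persisting one, how infections present at enrolment are handled, and which weekly biomarker value is used.

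**Cost.** Plan wording and a few data definitions. V.A records only that an infection occurred, so onset dates must be confirmed on the data collection sheet, which is not in the documents.

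**Limits to state.**
- Model (A) has modest power: 19–55% for a true 30–50% reduction under the assumptions above.
- Infection may lengthen stay. With 3 or 7 extra days per infection assumed, a true rate ratio of 0.70 per SD of selenium reads 0.71–0.72 with the offset.

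**Fallback.** If only any-infection data exist, use a binary model with few predictors plus days. The full list has 11 degrees of freedom (3 biomarkers, 2 for treatment, and 1 each for age, %TBSA, dietary selenium, sex, race and time to enrolment), or 12 with days. With 12 the model could not be estimated in 0%, 18% and 99% of simulated datasets at 67%, 87% and 98% infected; with 4 the figures were 0%, 7% and 97%. If almost all children are infected, report by arm descriptively.

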(Figure 1). All subjects consumed greater than the RDA for Se (Table 5). They also consumed more Se than recommended by the ASPEN (27).

Table 5. Dietary Se Intake and % AI According to Age

Age (years)	Number of Subjects	Mean Se Intake (ug/day)	Mean Se Intake (ug/kg/day)	% RDA
1-3	8	40	2.9	200
5-8	2	62	2.5	201
9-13	7	75	1.6	183
14-18	2	83	1.4	151

Plasma Se (mean = $1.08 \pm 0.34 \text{ } \mu\text{mol/L}$) did not change throughout the entire study. However, 82% of the total weekly samples were below the $1.35 \text{ } \mu\text{mol/L}$ plasma selenium level reported in healthy American children ages 1-18yrs (Figure 2). Higher plasma selenium was also correlated with a lower incidence of infection ($p = 0.043$).

The mean plasma glutathione peroxidase (GPx) level over the eight weeks was $3.29 \text{ Units/mg protein} \pm 1.42$. Furthermore, 40% of all weekly plasma GPx samples were below the $2.8-3.4 \text{ U/g protein}$ range established in healthy American girls ages 11-14 (34) . No statistical differences were found throughout the eight weeks.

There was no significant change in urinary selenium levels between weeks. The mean urinary selenium level throughout the eight-week study was $65.9 \text{ } \mu\text{g/L} \pm 50$, which is higher than the mean selenium intake from diet $60 \text{ } \mu\text{g/L} \pm 39$. A majority of the observed urinary selenium levels were higher than those reported ($28.7 \text{ } \mu\text{g/L} \pm 8.3$) in healthy American children ages 5-18 years (35).

In summary, these results indicate that selenium status in pediatric burn patients, as measured by plasma and urine selenium concentrations and plasma GPx activity, was inadequate throughout the eight weeks following thermal injury. Additionally, these results suggest that maintaining normal blood concentrations of selenium and GPx activity following burn injury reduce the incidence of infection. This data was presented at the American Burn Association Annual meeting in March 2007 and published in the Journal of Trauma in 2010.

Figure 1. Dietary Selenium. Selenium intake did not change significantly over the eight week study. Intake ranged from 100-400% the AI/RDA (based on age).

[figure not shown]
[figure not shown]

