- C. Another parameter that will be recorded is the occurrence of pneumonia or infection (bacterial or fungal) in the wound, blood, or urine, as defined by The National Nosocomial Infection Surveillance System (A localized or systemic condition that results from adverse reaction to the presence of an infectious agent(s) or toxin(s)) and clarified by the Infection Control Nurse. Specific definitions are as follows:

Urinary Tract Infections

a) Patient has at least 1 of the following signs or symptoms with no other recognized cause: fever ($>38^{\circ}\text{C}$), urgency, frequency, dysuria, or suprapubic tenderness
and
patient has a positive urine culture that is $\geq 10^5$ microorganisms per cm^3 of urine with no more than 2 species of microorganisms.

b) Patient has at least 2 of the following signs or symptoms with no other recognized cause: fever ($>38^{\circ}\text{C}$), urgency, frequency, dysuria, or suprapubic tenderness
and at least 1 of the following

- Positive dipstick for leukocyte esterase and/or nitrate
- Pyuria (urine specimen with $\geq 10 \text{ WBC/mm}^3$ or $\geq \text{WBC/high power field of unspun urine}$)
- Organisms seen on Gram stain of unspun urine
- At least 2 urine cultures with repeated isolation of the same uropathogen (gram-negative bacteria or *S. saprophyticu*) with $\geq 10^2$ colonies/mL in nonvoided specimens
- $\leq 10^5$ colonies/mL of a single uropathogen (gram-negative bacteria or *S. saprophyticu*) in a patient being treated with an effective antimicrobial agent for a urinary tract infection
- Physician diagnosis of a urinary tract infection
- Physician institutes appropriate therapy for a urinary tract infection

c) Patient 1 year of age has at least 1 of the following signs or symptoms with no other recognized cause: fever ($>38^{\circ}\text{C}$), hypothermia ($<37^{\circ}\text{C}$), apnea, bradycardia, dysuria, lethargy, or vomiting
and
patient has a positive urine culture that is $\geq 10^5$ microorganisms per cm^3 of urine with no more than 2 species of microorganisms

d) Patient 1 year of age has at least 1 of the following signs or symptoms with no other recognized cause: fever ($>38^{\circ}\text{C}$), hypothermia ($<37^{\circ}\text{C}$), apnea, bradycardia, dysuria, lethargy, or vomiting
and at least 1 of the following:

- Positive dipstick for leukocyte esterase and/or nitrate
- Pyuria (urine specimen with $\geq 10 \text{ WBC/mm}^3$ or $\geq \text{WBC/high power field of unspun urine}$)

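### The secondary infection analysis does not say which weekly selenium value enters, or that it must precede the infection, so an infection-driven fall in selenium could be read as low selenium raising infection risk

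*Combined protocol and SAP*

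**What the plan says.** Section II states: "The secondary hypothesis is that Se status is related to the incidence of infection among pediatric patients with burns". Specific aim 2 is "to determine the association between Se supplementation, biomarkers of Se status and indicators of stress and infection".

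The statistical text in section V.D plans an ordinal logistic regression for the relationship between "incidence of infection (categorized by burn, bloodstream, urinary tract infection, and PNA) and plasma selenium, urinary selenium, plasma GPX", with age, initial burn size and treatment group as further terms. Repeated measures are named there for the primary hypothesis only. The listed confounders are dietary selenium, age, sex, race, initial burn size and time from burn to enrolment. The list is open-ended, but neither an earlier infection nor C-reactive protein is named, although section V.C (Other Data) records the latter.

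On timing, section V.C says: "Plasma and urine Se and plasma Gpx will be measured weekly from the time of admission for a maximum of 8 weeks", or until near-complete wound closure. Section V.A says of infection: "Another parameter that will be recorded is the occurrence of pneumonia or infection (bacterial or fungal) in the wound, blood, or urine". It gives detailed case definitions but does not ask for a date of onset or link an infection to a selenium sample.

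**The concern.** A child can contribute up to eight values of each marker and can become infected in any week. The regression needs one marker value beside each infection outcome, and the plan leaves that choice open. A mean over the stay includes samples drawn after the infection began. A same-week pairing can include samples drawn during it. Under either choice the outcome can shape the predictor.

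The protocol itself treats acute injury as lowering selenium status: in the pilot (section I.B), 82% of weekly plasma samples were below the healthy reference although all children ate more than the RDA. A further fall with infection is a reasonable worry on that premise.

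The risk of misreading is also concrete. The pilot found "Higher plasma selenium was also correlated with a lower incidence of infection" (p = 0.043). No time order is reported for that correlation, yet the pilot summary takes it to suggest that keeping selenium and GPx normal lowers infection. Section I.C hopes the results will help in recommending supplements. The point concerns the marker-infection association, not the comparison of randomised groups.

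**Working it through.** **The plan's own figure.** n = 2(1.96 + 0.8416)^2 / (0.27/0.34)^2 = 24.89, rounded up to 25 per group, 75 in all. This reproduces, but it belongs to the primary hypothesis. No figure is given for the infection analysis.

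**Inputs for an illustration.** From the documents: 75 children, at most 8 weekly values, SD 0.34 umol/L. Assumed: intraclass correlation 0.45, weekly infection risk 9% or 20%, infection lowers selenium by 0.1 or 0.2 umol/L, selenium has no effect on infection. The predictor is the whole-stay mean, compared between children with and without infection.

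**Hand calculation.**
- SD of an 8-week mean: 0.34 x sqrt(0.45 + 0.55/8) = 0.245.
- Share ever infected: 1 - 0.91^8 = 0.53 (39.7 v 35.3 children), or 1 - 0.80^8 = 0.83 (62.4 v 12.6).
- SE of the difference: 0.245 x sqrt(1/39.7 + 1/35.3) = 0.0567, or 0.245 x sqrt(1/62.4 + 1/12.6) = 0.0756.
- Average weeks at or after first infection, in infected children: (8 - 0.91 x 0.53/0.09)/0.53 = 5.0, or (8 - 0.80 x 0.83/0.20)/0.83 = 5.6. As shares of 8 weeks: 0.62 and 0.70.
- z = fall x share / SE. The false-positive rate is about Phi(z - 1.96), plus a small opposite tail.

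| Weekly risk | Samples lowered | Fall 0.1 | Fall 0.2 |
|---|---|---|---|
| 9% | two (share about 2/8) | z 0.44, 7% | z 0.88, 14% |
| 9% | all later | z 1.10, 20% | z 2.20, 60% |
| 20% | all later | z 0.93, 15% | z 1.86, 46% |

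**Simulation over the same range.** About 7 to 21% for a 0.1 fall and 15 to 64% for a 0.2 fall, against a nominal 5%. Low ends correspond to a short fall, high ends to one that lasts.

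**Is it the single record per child that causes this?** No. A second simulation varied weekly risk from 10 to 30% and let the fall affect only the week of infection.
- One record per child, with an ordinal infection count on the 8-week mean (within-child correlation 0.3 to 0.7): 7 to 16% false positives for a fall of 0.5 SD (0.17 umol/L) and 19 to 44% for 1 SD (0.34).
- Weekly records pairing same-week selenium and infection (correlation 0.5): 95 to 100%.
- Weekly records using the previous week's selenium (correlation 0.5): 3 to 8%.

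The missing element is the time order.

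**Is a lag enough?** Not when children differ in susceptibility and have repeat infections, because a value lowered by one infection then predicts the next. With such variation and a 0.2 fall, the lagged model over all infections gave 10 to 17% false positives. Restricted to first infections it gave 4 to 7%.

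**The case against.** The plan speaks of a relationship and an association, not of prediction. If infection lowers selenium, an inverse association is real, and reporting it would not be an error against the hypothesis as worded. This stands: the false-positive rates above apply only to the reading that low selenium raises risk. The pilot summary shows how easily that step is taken, though it says only that the results suggest it.

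A reader might infer that the plan uses one record per child. It does not say so. An ordinal model can be fitted to repeated records, and a list of four sites, more than one of which can apply to the same child, does not settle the unit. A reader might also infer that the trial would report low selenium as predicting infection. The documents do not support that either.

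No passage says that infection lowers selenium, and mean plasma selenium in the pilot did not change over the eight weeks. That is a group-level result and does not exclude falls within infected children.

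The infection rate matters too. One adult burn trial in Table 7 reports 2 infections per supplemented patient in 30 days. At a constant rate this gives a weekly risk of 1 - exp(-2 x 7/30) = 37%, and 1 - exp(-2 x 56/30) = 98% infected by week 8. About 70% of simulated trials then had fewer than 3 uninfected children. In the rest, a lasting 0.2 fall gave about 18% false positives, well below the figures at lower rates. Finally, the whole-stay illustration is an unadjusted comparison giving every child 8 values, whereas the planned model is adjusted and many children will leave earlier. All this limits the size; none of it supplies the missing time order.

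**Conclusion.** The concern holds as a gap in specification with a real consequence. The plan does not state the record unit, which weekly marker value enters, or that it must precede the infection. Both obvious ways of filling the gap let an infection-driven fall in selenium appear as an inverse association.

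The 7 to 21% and 15 to 64% ranges are illustrations. They rest on an assumed fall, its assumed duration and an assumed weekly risk of 9 to 20%, and should not be quoted as the error rate of the plan. The conclusion that an ordered analysis is better does not depend on the exact size. This should be changed before the data are analysed. It affects the secondary hypothesis only and leaves the primary comparison untouched.

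**What to change.** In section V.D, define the marker-infection analysis on child-week records up to each child's first infection:
- The outcome is onset of first infection in that week.
- The predictor is the last plasma selenium drawn before onset; urinary selenium and GPx are analysed separately in the same way.
- Adjust for study week, age, initial burn size and treatment group, with standard errors clustered by child.
- If later infections are included, adjust for prior infection.
- Add the date of infection onset to the items recorded under section V.A, which at present promises only occurrence.

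No extra samples or visits are needed. The cost is precision: weeks with no earlier marker value, including first-week infections, and repeat infections drop out. At 9% weekly risk, 0.09/0.53 = 17% of infected children have their first infection in week 1, leaving about 75 x (0.53 - 0.09) = 33 usable first infections. At 20%, the share is 0.20/0.83 = 24%, leaving about 75 x (0.83 - 0.20) = 47. These counts assume full 8-week follow-up and will be lower with early exits.
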